#### 6.4.4.5 FEV1

The FEV1 will be measured at Screening (Visit 1B/C), prior to and 30 minutes after Study Medication Administration (Visits 3A-3H), at the End of Dosing Assessment (Visit 3I), and at the end of PAC1, PAC2 and PAC3 (Visits 4B, 4D and 4F). Asthmatic subjects should not use their asthma medication for a minimum of 4 hours prior to the spirometry assessment.

At each assessment FEV1 will be measured according to the American Thoracic Society guidelines with the subject sitting and the highest reading will be recorded in the eCRF.

#### 6.4.4.6 Injection Site Reactions

At each study medication administration (Visits 3A-3H), the injection site will be examined immediately prior to and 30 minutes after the administration of study drug for signs of reaction. Reactions should be graded on a 5 point (0-4) scale for each of the following parameters, as shown in Section 6.2.2.1: pain, tenderness, redness, swelling.

At Visits 3B-3H and at the End of Dosing Assessment (Visit 3I), this will include examination of the previous injection site.

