Period 1, Consent, Screening and Baseline Allergy Evaluation: Rhinoconjunctivitis scores and allergy rescue medication usage will be collected. After consent has been obtained, screening will be conducted in a staged approach to minimise the number of investigations that a potentially ineligible subject undertakes. Firstly, a blood sample will be taken for measurement of IgE to Der f, Der p and relevant perennial allergens. This visit (visit 1A) may be performed during a seasonal allergen period and before the start of additional screening activities. Potential subjects with IgE above the required levels will complete, between visits 1A and visit 1B/C, a paper diary (pDiary) of symptoms for 1 week before additional screening activities are performed. Subjects found to be eligible based on these two steps will undergo screening up to a maximum of 8 weeks before randomisation which may consist of 1 or 2 visits to the clinic, at the Investigator's discretion. In exceptional circumstances, due to reasons beyond the control of the Investigator and/or subject (for example extreme weather), this 8 week period may be exceeded; however this requires documented approval by the Sponsor. Suitable subjects will record Baseline rhinoconjunctivitis symptom scores

VERSION FINAL 4.0 CONFIDENTIAL PAGE 21 OF 92

(RSS) using a 4-point categorical scale and RMS for a 3-week period in an eDiary before randomisation. The completion of the p Diary over 7 days, allergy screening and the BAE period will take place outside of any and all relevant seasonal allergy periods for each individual subject.

Period 2, Study Medication Administration: Subjects meeting the inclusion/exclusion criteria will be randomised to either one of the 3 active treatment groups or the placebo group in equal proportions.

A total of 8 doses of HDM-SPIRE or placebo will be administered, one dose every 4 weeks (±2 days), for a total duration of 28 weeks as shown in Table 2.

Table 2Dosing Schedule

Visit	3A	3B	3 C	3D	3E	3F	3G	3Н
Week (± 2 days)	0	4	8	12	16	20	24	28
Treatment Groups	Treatment Groups							
Placebo	P	P	P	P	P	P	P	P
HDM-SPIRE 4 x 12 nmol	X	X	X	X	P	P	P	P
HDM-SPIRE 4 x 12 nmol, two courses	X	X	X	X	X	X	X	X
HDM-SPIRE 4 x 20 nmol	X	X	X	X	P	P	P	P

X = Active doses; P = Placebo doses

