### 5.5.2 Missed Dose

Dosing visits should be scheduled at intervals of 4 weeks from Visit 3A, with a window of  $\pm 2$  days. In the event that a visit needs to be rescheduled it may be rearranged such that it falls no later than 7 days before or after the original 4 week interval from the prior dose. On successful completion of a rearranged dosing visit the next dose should then be scheduled as per the original schedule ( $\pm 2$  days).

If it is not possible to reschedule within 3-5 weeks of the previous dose then it should be considered a missed dose and the next dose should be scheduled in accordance with the original schedule (± 2 days) provided that this does not result in an interval between any two doses of less than 3 or greater than 5 weeks.

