#### Pre-dose assessments:

- Recording of any AEs.
- Recording of any changes to concomitant medication since last visit.
- Urine pregnancy test (for females and which must be negative for the subject to continue in the study).
- Examination of the injection site from previous administration (not relevant for Visit 3A) with recording of any injection site reaction on the following scale (FDA Guidance for Industry 2007) (Table 7):

	Grade 0	Grade 1	Grade 2	Grade 3	Grade 4
Pain	None	Does not interfere with activity	Repeated use of non-narcotic pain reliever >24 hours or interferes with activity	Any use of narcotic pain reliever or prevents daily activity	Emergency room visit or hospitalization
Tenderness	None	Mild discomfort to touch	Discomfort with movement	Significant discomfort at rest	Emergency room visit or hospitalization
Erythema/ Redness *	None	2.5 – 5 cm	5.1 – 10 cm	>10 cm	Necrosis or exfoliative dermatitis
Induration/ Swelling**	None	2.5 – 5 cm and does not interfere with activity	5.1 – 10 cm or interferes with activity	>10 cm or prevents daily activity	Necrosis

**Table 7** Grading of Injection Site Reactions

- Spirometry (FEV1) [asthmatic subjects should not take their  $\beta$  agonist asthma medication for a minimum of 4 hours prior to spirometry]. FEV1 must be  $\geq$ 70% of predicted for a subject to be dosed.
- In the event that the FEV1 is less than 70% of predicted the subject's asthma medication use should be reviewed and any appropriate adjustments made. The dosing visit should then be rescheduled within 5 days. A dosing visit may only be rescheduled once, after which time it becomes a missed visit.
- Vital signs (seated or semi-recumbent).
- Blood sample for biomarker analysis (OPTIONAL sub-study ONLY at Visit 3A see Section 6.4.4.7)

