#### Post-dose assessments:

- Spirometry (FEV1) will be performed 30 minutes after injection. Asthmatic subjects should not take their asthma medication for a minimum of 4 hours prior to spirometry.
- Vital signs measured 30 minutes after injection (seated or semi-recumbent).
- Examination of the injection site between 30 minutes after injection, with findings recorded using the scale above.
- Blood sample for tryptase will be taken only in the event of a suspected anaphylactic response. The initial sample should be taken approximately 1 hour after the attack, with a further sample at approximately 3 hours and then repeated every 3 hours until the Investigator is satisfied that the subject may be discharged. Note: blood sampling

VERSION FINAL4.0 CONFIDENTIAL PAGE 50 OF 92

\* In addition to grading the measured local reaction at the greatest single diameter, the measurement should be recorded as a continuous variable. \*\* Induration/Swelling should be evaluated and graded using the functional scale as well as the actual measurement.

**for tryptase must not delay initial resuscitation**. Any subject that experiences a suspected anaphylactic reaction must also have a sample collected for assay of tryptase at the next dosing visit or the end of study visit.

- Recording of any AEs prior to discharge.
- Issue new pDiary prior to discharge and instruct subjects to record details of injection site reactions in the 7 days after each dose.

Post-treatment assessments made within  $\pm 5$  minutes of the nominal times will not be regarded as a protocol deviation. Where more than one assessment is scheduled at a nominal time, the assessments will be conducted in the following order:

- 1. Vital signs
- 2. Spirometry (FEV1)
- 3. Examination of injection site

Subjects will be asked to complete a pDiary from Visit 3A to Visit 3I of AEs and concomitant medications. The pDiary will be checked at all visits and information entered into the eCRF. The pDiary must then be retained in the Investigator Site File.

The Investigator will assess the need for any asthmatic subject to be provided with a salbutamol/albuterol inhaler and/or peak flow meter at Visit 3A before leaving the clinic.

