## 7.0 STATISTICAL CONSIDERATIONS

## 7.1 Data Management and Quality Assurance

All data in the study will be captured and maintained in a secure, validated electronic data capture (EDC) system. Study site staff will enter the data for each subject on an eCRF. The laboratory data and eDiary card data will be transferred electronically to Data Management and reconciled with the data entered at site. The subjects will enter their RSS, ASS and use of Rescue Medication directly into the study eDiary.

Additionally a pDiary Card will be used to aid the collection of AEs, concomitant medications and home environment changes. The Investigator will review the pDiary Card at each study visit and the data will be transcribed onto the eCRF.

The eCRF and eDiaries will contain automated edit checks to ensure the quality, integrity, accuracy and completeness of the data entered. The Study Monitor will periodically review the eCRF input and source document verify eCRF data. The medical monitor may examine eCRF and diary card data for preliminary medical review.

The eCRF data will be maintained in a validated study database with an audit trail of all changes that are made to the database, including the reason for the data change. Adverse events will be coded using a standard dictionary (Medical Dictionary for Regulatory Activities [MedDRA]), while concomitant medications will be categorised using the World Health Organisation drug dictionary.

Creation and validation of the EDC system and management of the data will be conducted in accordance with title 21 of the Code of Federal Regulations Part 11 and the US FDA Guidance for Industry on Computerised Systems used in Clinical Investigations. Methods used to ensure the quality and integrity of the data will be documented in the Data Management Plan, which will be approved by the Sponsor.

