#### **16.7.2. LOCAL REACTION AT INJECTION SITE**

Grading of each of the four components of an injection site reaction (pain, tenderness, induration/swelling and erythema/redness) is to be categorised as 'Grade 0', 'Grade 1', 'Grade 2', 'Grade 3' or 'Grade 4' in accordance with the severity of the reactions as specified in Table 7, Section 6.2.2.1 of the protocol.

Frequency (n) and percentage (%) of subjects with local reactions at the injection site are to be summarised by reaction grade and visit for each treatment group.

All injection site reactions are to be listed.

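### Injection-site reactions in the 7 days after each dose have no stated route to a Table 7 grade or to the SAP 16.7.2 table

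*Protocol*

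**What the plan says.** Protocol 6.4.4.6 sets the schedule for Visits 3A to 3H: "the injection site will be examined immediately prior to and 30 minutes after the administration of study drug for signs of reaction". It adds: "At Visits 3B-3H and at the End of Dosing Assessment (Visit 3I), this will include examination of the previous injection site". Each injection site is therefore graded on the 0 to 4 scale of Table 7 (Section 6.2.2.1) twice, at 30 minutes and at the following visit.

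For the days in between, the post-dose list in Section 6.2.2.1 tells staff to issue a new paper diary and "instruct subjects to record details of injection site reactions in the 7 days after each dose". It does not say which details, and it does not refer to Table 7.

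Section 7.1 describes the diary's purpose: "a pDiary Card will be used to aid the collection of AEs, concomitant medications and home environment changes". Injection-site reactions are not named as a separate item there, in the Visit 3I transfer list (6.2.2.2) or in the list of diary items for eCRF entry (8.4.1).

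SAP 16.7.2 says that local reactions "are to be summarised by reaction grade and visit for each treatment group". It also calls for a listing of all injection-site reactions.

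**The concern.** The protocol asks for a 7-day record after every dose, so it treats that week as informative about local tolerability. Yet the graded table is fed by examinations that fall outside it. If reactions develop over hours or days and then clear, the graded table would describe the site shortly after the needle and again roughly a month later, and not at its worst.

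This matters most for the 20 nmol arm. Protocol 1.3.1 gives equivalent safety and tolerability of a unit dose above 12 nmol as part of that arm's rationale, and says that 12 nmol is the highest unit dose evaluated so far. A graded comparison that can miss the peak is weak evidence on that question, and likewise on one course against two.

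Table 7 grades also have a second use. Sections 5.5.1 (dose reduction) and 4.6 (discontinuation of dosing) both turn on a grade 3 or 4 injection-site reaction. If it is unclear whether a diary entry carries a grade, two sites could handle the same entry differently.

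**Working it through.** The plan states no figure on this point, so the check is one of timing and of tracing the data.

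**Timing.** Inputs are the 4-weekly interval with its 2-day window (Protocol 3.1 and 6.2.2.1; Visit 3I has the same spacing after the last dose), the 7-day diary period (6.2.2.1), and the limit in 5.5.2: "If it is not possible to reschedule within 3-5 weeks of the previous dose then it should be considered a missed dose".

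- Next look at the same site: 28 − 2 = 26 to 28 + 2 = 30 days after the dose.
- Gap from the end of the diary week to that look: 26 − 7 = 19 to 30 − 7 = 23 days.
- With rescheduling, the interval is 21 to 35 days, so the gap is 21 − 7 = 14 to 35 − 7 = 28 days.
- Scheduled injection-site examinations between 30 minutes and the next dosing visit or 3I: none. Visit 4A at week 18 falls 2 weeks after the week-16 dose, but Table 5 schedules no site examination there.
- Over the course: 8 doses × 7 days = 56 diary days per subject with no scheduled grading.

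**What Table 7 needs.** One limb of grade 2 pain reads "Repeated use of non-narcotic pain reliever >24 hours or interferes with activity". The 24-hour part cannot be met 30 minutes after the injection. Grade 4 pain and tenderness are defined by emergency room attendance or hospital admission, which again calls for later history. Redness and swelling are graded on measured diameter, and the text asks for no diary measurement.

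**Where a day 1–7 reaction can go.**

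| Route | What the documents say | Table 7 grade? |
|---|---|---|
| 30-minute examination | Precedes the reaction | Yes, but too early |
| Pre-dose examination at the next visit (6.2.2.1) | Any reaction from the previous administration is recorded on Table 7, under an instruction to examine the site | Unclear whether a cleared reaction is graded from history |
| Diary to eCRF (6.2.2.1, 7.1) | Diary is reviewed at visits and transcribed; site reactions not named as a separate item | None stated |
| Adverse event tables (SAP 16.1) | Severity is mild, moderate or severe; summarised by system organ class and preferred term | No |
| SAP 16.7.2 listing | All site reactions listed | Not a comparison between arms |

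Protocol 6.4.4.4 converts CTCAE grade increases into adverse event severity. Nothing comparable links Table 7 with adverse event severity, so the adverse event route does not supply the grade that 16.7.2 tabulates.

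**Attribution.** At Visits 3B to 3H there are two looks, one at the previous site before dosing and one at the new site 30 minutes after. SAP 16.7.2 does not say which of them a visit's grade represents. At Visit 3E in both 4-dose arms, the first concerns the last active dose and the second the first placebo dose (Protocol Table 2).

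**The case against.** The strongest answer is that the information is not lost. The diary is checked at every visit and transcribed to the eCRF. Site reactions are not among the exclusions from the adverse event definition, so they can appear in the treatment-emergent tables by severity and relationship, with a separate summary for onset within 24 hours of any dose. All reactions are listed. The pre-dose assessment covers any reaction from the previous administration, and analgesic use, emergency visits and admissions can be scored then from history. The primary safety endpoint (Protocol 7.5.4) is the number of adverse events and of subjects with them, not the local-reaction table, and no inferential safety tests are planned.

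Much of this stands. A reader might infer that day 1–7 reactions exist only on paper and are never graded or summarised. The documents do not support that, given the transcription, the adverse event route and the listing. A reader might also infer that sites would give the next full dose after an unnoticed grade 3 reaction. That does not follow either: Section 5.5.1 applies when a subject experiences such a reaction, Section 4.6 when doses result in one, and neither limits the source to a scheduled examination.

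What the objection does not supply is a sentence that gives the diary entries a Table 7 grade or places them in the 16.7.2 table. Grading from history at the next visit is a possible reading, but Sections 6.2.2.1 and 6.4.4.6 both frame that step as an examination of the site, and sites could differ. The diary page and the injection-site eCRF form are not part of the documents. They may settle some of this, but the protocol and SAP do not.

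**Conclusion.** The point holds as a gap in the graded local-tolerability summary. Scheduled Table 7 gradings are at 30 minutes and about 4 weeks (26 to 30 days, or 21 to 35 with rescheduling). The 7-day entries have no stated path to a Table 7 grade, to a dose or to the 16.7.2 table. A reaction that peaks after 30 minutes and clears before the next visit can therefore be missing from the graded comparison, although it may appear as an adverse event and in the listing.

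The size is unknown, because the documents give no rate of delayed reactions. It is tempting to say that the table would be biased towards no difference between regimens, or that it is the trial's main tolerability comparison. The documents support neither. The conclusion assumes that at least some reactions follow that time course, and that no form outside the documents already assigns the grade. It is a worthwhile, low-cost improvement and not a flaw in the primary safety endpoint.

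**What to change.** 1. In Protocol 6.2.2.1, 6.2.2.2 and 6.4.4.6, have the worst Table 7 grade per component (pain, tenderness, redness, swelling) since the last dose recorded in the eCRF when the diary is reviewed, before dosing at Visits 3B to 3H and at Visit 3I. Record its date and the dose to which it belongs.
2. In SAP 16.7.2, add a summary of the worst grade per component from 30 minutes to day 7 after each dose, by treatment group, beside the by-visit table. State which of the two examinations a visit's grade in the existing table represents.
3. Separately, reconcile Protocol 4.6, 5.5.1, 6.2.2.1, 6.2.2.2, 6.4.4.6, 7.1 and 8.4.1 on which recorded grades the dose-reduction and discontinuation passages refer to. That choice is the sponsor's, and no clinical rule is proposed here. It should be settled together with item 1, because item 1 creates a further recorded grade.

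The cost is a few eCRF fields per dosing visit and one table, since subjects already record the reactions. The downside is that part of the grade rests on subject report, and diameter-based grades may be incomplete if the diary does not ask for a measurement.

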## 6.4.4.7 OPTIONAL Biomarker Analysis

Blood samples for biomarker analysis will be obtained at Visit 3A and at Follow-Up (Visit 5). These samples will ONLY be taken from subjects at participating sites in Canada and US. Subjects will be required to sign a separate consent form to participate in this optional substudy.

A blood sample (20 mL) will be collected and stored for future analysis. A biomarker analysis plan will be on file prior to the start of the biomarker analysis.

VERSION FINAL4.0 CONFIDENTIAL PAGE 65 OF 92

## 7.0 STATISTICAL CONSIDERATIONS

## 7.1 Data Management and Quality Assurance

All data in the study will be captured and maintained in a secure, validated electronic data capture (EDC) system. Study site staff will enter the data for each subject on an eCRF. The laboratory data and eDiary card data will be transferred electronically to Data Management and reconciled with the data entered at site. The subjects will enter their RSS, ASS and use of Rescue Medication directly into the study eDiary.

Additionally a pDiary Card will be used to aid the collection of AEs, concomitant medications and home environment changes. The Investigator will review the pDiary Card at each study visit and the data will be transcribed onto the eCRF.

The eCRF and eDiaries will contain automated edit checks to ensure the quality, integrity, accuracy and completeness of the data entered. The Study Monitor will periodically review the eCRF input and source document verify eCRF data. The medical monitor may examine eCRF and diary card data for preliminary medical review.

The eCRF data will be maintained in a validated study database with an audit trail of all changes that are made to the database, including the reason for the data change. Adverse events will be coded using a standard dictionary (Medical Dictionary for Regulatory Activities [MedDRA]), while concomitant medications will be categorised using the World Health Organisation drug dictionary.

Creation and validation of the EDC system and management of the data will be conducted in accordance with title 21 of the Code of Federal Regulations Part 11 and the US FDA Guidance for Industry on Computerised Systems used in Clinical Investigations. Methods used to ensure the quality and integrity of the data will be documented in the Data Management Plan, which will be approved by the Sponsor.

#### 7.1.1 Rescreening Data

In a limited set of circumstances, subjects will be permitted to be rescreened for the study (See Section 4.5). All data from these subjects, both the original and repeat assessments, will be entered into the study database. For those parameters where repeat assessments are made, the repeat assessment will be used in data summaries. The original assessments will be listed only.

## 7.2 Sample Size

The study will recruit approximately 660 subjects (approximately 165 per group). Based on the data from observational study TH003, if a mean CS of 1.6 is observed for the placebo group, and a mean CS of 1.28 for the active group, the expected treatment difference of 0.32 will be a 20% improvement from placebo. The statistical model will include the baseline CS as a covariate, taking this into account a standard deviation of 0.986 is assumed, so that a sample of 150 patients will have 80% power to detect a statistically significant difference in treatment.

Other data sources result in sample size estimates that range from 103/group (based on the TRSS data from Study TH002) through to 200/group (based on symptom scores adjusted for medication use in a study of sublingual HDM immunotherapy [Bergmann et al, 2013]). These data support the assumptions from Study TH003 and indicate that a difference of 20% between placebo and active treatment will be observed with a sample size of 150 subjects per group. It is estimated that up to 10% of subjects may drop-out before PAC3 or have missing data during PAC3. Consequently, approximately 660 subjects in total will be randomised.

## 7.3 Interim Analysis

No interim analysis is planned for this study.

## 7.4 Analysis Populations

### 7.4.1 Intent-to-Treat Population

The population for the efficacy analyses will be the Intent-to-Treat (ITT) population consisting of all subjects who are randomised, who have received at least one dose of study medication. Subjects will be reported by the treatment they were randomised to. This is the primary population for the study, and all the primary and secondary efficacy analyses will be based on the ITT population.

